During the 16-week Induction Period, 312 patients will be randomised 2:1 to either 250 mg lebrikizumab (loading dose of 500 mg given at Baseline and Week 2) or placebo by SC injection Q2W. Randomisation will be stratified by previous use of dupilumab, age (adolescent patients aged ≥ 12 to < 18 years will make up 12.5% of the overall population compared to adults aged ≥ 18 years) and baseline disease severity (IGA 3 versus 4). During the first 4 weeks of treatment as well as at Week 8, Week 12, Week 16, and Week 18 study drug injection will be administered in the clinic. Patients will have the option to self-administer study drug or get it administered by a caregiver outside the study site during weeks in which no on-site clinic visit is scheduled from Week 4 onward according to [Table 1](#). Patients (and/or caregivers) will be trained on injecting study drug until competency has been demonstrated.

In case a patient is not willing to self-inject, their caregiver is not willing to do the injection, or the patient or caregiver does not demonstrate appropriate ability to do the injection, the clinic staff may administer all study drug injections throughout the study at the clinic.

All enrolled patients are required to start treatment with mid- or low-potency TCS at Baseline and continue it throughout the study as described in [Section 9.9.2](#).

After completion of the Week 16 visit, patients will enter the Maintenance Period:

- Patients who received lebrikizumab 250 mg Q2W during the Induction Period will continue to receive lebrikizumab 250 mg Q2W during the Maintenance Period
- Patients who received placebo Q2W during the Induction Period will receive lebrikizumab 250 mg Q2W during the Maintenance Period

Patients who received placebo during the Induction Period will receive loading doses of lebrikizumab (500 mg) at Weeks 16 and 18 during the Maintenance Period.

To allow patients in the placebo arm to receive these lebrikizumab loading doses during the Maintenance Period, the blinding will be maintained at Week 16 and Week 18. Therefore, the study will be open-label from Week 20 onward, as summarised in

Table 4.

Table 4. Dosing Schedule During Maintenance Period

Randomised at Baseline to	Double-blind Dose at Week 16	Double-blind Dose at Week 18	Open-label Treatment After Week 20

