9.1 Identity of Trial Investigational Medicinal Product(s)

Investigational medicinal product (IMP) manufacturing, labelling, packaging, and release will be implemented following good manufacturing practice (GMP) guidelines.

Test Investigational Medicinal Product

Substance Code/Name	Lebrikizumab
Route of Administration	Subcutaneous
Dosage Form	Solution for injection, containing 125 mg/mL lebrikizumab. Supplied as a sterile prefilled syringe with a pre-assembled needle safety device (PFS-NSD)
Unit Dose/Strength	Each prefilled syringe is intended for a single 2 mL dose (250 mg)
Packaging Description	White folding carton with partition (167 x 54 x 40 mm) CCI 

Placebo Investigational Medicinal Product

Substance Code/Name	The placebo solution is identical in appearance and volume to the active solution except that it does not contain lebrikizumab
Route of Administration	Subcutaneous
Dosage Form	Solution for injection, containing the same excipients as the respective active lebrikizumab. Supplied as a sterile

prefilled syringe with a pre-assembled needle safety device (PFS-NSD)

Unit Dose/Strength Each prefilled syringe is intended for a single 2 mL dose

Packaging Description White folding carton with partition (167 x 54 x 40 mm)

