10.6.2 Reporting of Adverse Events

AEs either reported by the patient or observed by the Investigator must be recorded on the AE page of the eCRF and should be described in the following manner:

- The nature of the AE will be described in precise, standard medical terminology (ie, not necessarily the exact words used by the patient). If known, a specific diagnosis should be recorded instead of listing signs and symptoms (eg, allergic contact dermatitis).
- The duration of the AE will be described by the start date and end date.
- The intensity of the AE will be described in terms of mild, moderate or severe according to the Investigator's clinical judgment. And assign to 1 of the following categories:
 - **Mild:** Awareness of event, symptoms or signs, but easily tolerated (acceptable).
 - **Moderate:** Sufficient discomfort and interferes with usual activity (disturbing).
 - **Severe:** Incapacitating with inability to do normal daily living activities or significantly affects clinical status, and warrants intervention (unacceptable).
- The causal relationship of the event to the use of the IMP will be described as:
 - **Not related:** Event or laboratory test result abnormality, definitely not related to study drug, or as related to another drug, chemical, or underlying disease.
 - **Unlikely related:** Event or laboratory test result abnormality, with a time relationship to study drug administration that makes a relationship improbable; disease or other drugs, chemicals or underlying disease provide plausible explanations.
 - **Possibly related:** Event or laboratory test result abnormality with a reasonable time relationship to study drug administration; could also be explained by underlying disease or other drugs or chemicals; information on drug withdrawal may be lacking or unclear.
 - **Related:** Event or laboratory test result abnormality with a reasonable time relationship to study drug administration, unlikely to be attributed to underlying disease or other drugs or chemicals; response to withdrawal clinically reasonable (positive dechallenge).

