Possibly related and related terms will be considered "related" for reporting purposes. If the events are assessed as unlikely related or not related to the suspect IMP, the event does not qualify for reporting purposes. In the absence of information on causality from the reporting Investigator, PPD will immediately contact the reporting Investigator to request a causality assessment. The case will be updated with the follow-up information and reported accordingly. If no causality is provided by the Investigator, the Sponsor assessment will be considered for submission purposes.

- The outcome of the event will be described as:
 - Recovered/resolved
 - Recovering/resolving
 - Recovered/resolved with sequelae
 - Not recovered/not resolved
 - Fatal
 - Unknown
- The action taken on the study drug will be captured as:

- Drug withdrawn
- Not applicable

AEs will be collected only once with its maximum severity, except when the AE started before first IMP administration, persisted after it and worsened in severity any time after first IMP administration. In this latter case, the AE will be collected with each respective severity. The AE term recorded must be exactly the same in the different time points where AE is reported in the eCRF.

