If the start date of any TEAE is incomplete or missing, the event will be assumed to be in the Induction Period, unless the incomplete start date (month and/or year) clearly indicates that the event started on or after the first dosing in Maintenance Period.

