10.1. Adverse Events

Adverse events (AEs) will be coded using MedDRA Version 24.1 or higher. In the event of a missing/incomplete start or stop date associated with an adverse event, only the treatment-emergence will be imputed using the algorithm described in エラー! 参照元が見つかりません。 [section 7.3.2](#). Dates will not be imputed.

A TEAE is any AE that newly appeared, or worsened in severity following initiation of study medication until last follow-up visit. Only TEAE will be included in the summary tables, but all AE will be included in the listings.

Following tables will be produced:

- An overall summary of the number and percentage of patients reporting TEAEs, Adverse Events of Special Interest (AESI), serious TEAEs, Suspected Unexpected Serious Adverse Reactions (SUSARs), TEAEs leading to study drug discontinuation, related TEAEs, related SAEs and Deaths.
- Incidence of AEs (AEs including TEAEs, SAEs, related TEAEs, related SAEs, TEAEs leading to study treatment discontinuation, AESIs and deaths)
- TEAEs overall and by system organ class and preferred term

This document is confidential.

- TEAEs by severity (Mild, Moderate, Severe), overall and by system organ class and preferred term
- TEAEs by relationship to study treatment (unrelated vs. related), overall and by system organ class and preferred term
- TEAEs leading to study drug discontinuation, overall and by system organ class and preferred term
- TEAEs leading to death, overall and by system organ class and preferred term
- Serious Adverse Events, overall and by system organ class and preferred term
- AESIs by severity (Mild, Moderate, Severe), overall and by preferred term
- AESIs by relationship to study treatment (unrelated vs. related), overall and by preferred term
- SUSARs, overall and by system organ class and preferred term

AEs possibly related and related to study medication will be combined for the "related" summaries.

If a patient met the same AE more than one time, AE will be counted only once with the maximum of severity.

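### An adverse event that starts on placebo and worsens after the Week 16 switch has one record, with its Induction start date and the severity reached on lebrikizumab, so it would be tabulated as a placebo-period event at that severity

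*Protocol*

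**What the plan says.** **Recording.** Protocol 10.6.2 states that "AEs will be collected only once with its maximum severity, except when the AE started before first IMP administration". The exception has two further conditions: the AE "persisted after it and worsened in severity any time after first IMP administration". Then, "In this latter case, the AE will be collected with each respective severity". On dates, the same section says only that "The duration of the AE will be described by the start date and end date".

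**What the first IMP dose is.** Protocol 9.1 lists a "Placebo Investigational Medicinal Product" next to the test product, so for a placebo patient the first IMP dose is the Day 1 placebo injection.

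**The switch.** Protocol 7.1: "Patients who received placebo during the Induction Period will receive loading doses of lebrikizumab (500 mg) at Weeks 16 and 18".

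**Treatment emergence.** SAP 10.1: "A TEAE is any AE that newly appeared, or worsened in severity following initiation of study medication until last follow-up visit". Protocol 11.8.4 also refers to the first dose of study drug. Neither sets a new reference point at Week 16.

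**Period and group.** SAP 10 reports safety as lebrikizumab against placebo up to Week 16, and as Lebri-Lebri against Placebo-Lebri afterwards, with separate Induction, Maintenance and combined tables. The only text that places an AE in a period is in SAP 7.3.2: "If the start date of any TEAE is incomplete or missing, the event will be assumed to be in the Induction Period", unless the partial date clearly shows a start at or after the first Maintenance dose. For medications with the same ambiguity, SAP 7.3.3 counts them in both periods.

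**Worsening.** Protocol 10.6.3 says that worsening of a known abnormality, found on a safety assessment after IMP and considered clinically relevant, should be reported as an AE. It does not say how this fits with the one-record rule.

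**The concern.** The protocol splits an AE record at the change from no drug to study drug. In the placebo arm the change that matters for lebrikizumab safety comes at Week 16, and nothing splits the record there.

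Take a placebo patient with mild conjunctivitis from Week 12 that becomes severe at Week 20. Under the one-record rule the site holds a single entry, graded severe and starting at Week 12. Read by start date, that is a severe TEAE on placebo, and the Maintenance tables show nothing.

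The Week 16 comparison is the only placebo-controlled safety evidence in the trial. SAP 10.1 tabulates TEAEs and AESIs by severity, and SAP 10.5.3 does so for conjunctivitis. A placebo column that contains severities reached on lebrikizumab is not a clean control, and Maintenance tables that omit worsening after the switch understate what followed the first active dose. The analysis cannot repair this, because the AE record has no date of worsening.

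**Working it through.** There is no planned figure to reproduce. The check follows an AE through the recording rule, the dates on its record, the TEAE definitions and the safety periods, for each possible onset.

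| Case | Onset | Worsens | Records under Protocol 10.6.2 | Where it falls if placed by start date |
|---|---|---|---|---|
| a | Placebo arm, after first dose and before the Week 16 injection | After the switch | One, at maximum severity | Placebo Induction column, at the severity reached on lebrikizumab; no Maintenance TEAE |
| b | Placebo arm, before first dose | After the switch | One per severity (exception applies) | The worsening has its own record and need not fall in the placebo period |
| c | Placebo arm, after the Week 16 injection | Any time | One | Maintenance; correctly placed |
| d | Lebrikizumab arm, after first dose and before Week 16 | After Week 16 | One, at maximum severity | Lebrikizumab Induction column, at a severity reached later on the same drug |

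Only case a attributes severity to the wrong treatment. Case d attributes it to the wrong period, and it matters because it enters the other side of the Week 16 contrast.

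**Direction.** Planned arm sizes are 104 placebo and 208 lebrikizumab (Protocol 11.1). The event counts below are assumed for illustration only. Suppose the true severe-AE counts up to Week 16 are 2/104 = 1.9% and 4/208 = 1.9%, a difference of 0.

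- Only placebo patients have later worsening pulled back, 3 events: (2 + 3)/104 = 4.8%. Lebrikizumab minus placebo = 1.9 − 4.8 = −2.9 points.
- Both arms in proportion, 3 and 6 events: 5/104 = 4.8% and (4 + 6)/208 = 4.8%. Difference 0.
- Only lebrikizumab patients, 6 events: 10/208 = 4.8%. Difference = 4.8 − 1.9 = +2.9 points.

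The sign therefore depends on how often ongoing AEs worsen after Week 16 in each arm, which the documents do not give.

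**Timing.** The first lock comes once all patients have finished Induction (SAP 2.2). Protocol section 1 plans about 24 months in total, roughly 104 weeks, and up to 72 weeks per patient. That leaves 104 − 72 = 32 weeks of enrolment. When the last patient reaches Week 16, the first is at about Week 32 + 16 = 48. Unless a data cut excludes later updates, the first lock can already hold severities reached after the switch, and an Induction severity table rerun at a later lock could differ from the first.

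**The case against.** The strongest case on the other side has five parts.

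1. **Start-date placement is not stated for complete dates.** This is correct. It is a strong inference from SAP 7.3.2, which uses the start date to settle the period when that date is incomplete. The plan gives no other rule.

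2. **Protocol 10.6.3 may already call for a new entry.** It may, for clinically relevant worsening found on safety assessments. But it does not say that it overrides 10.6.2, so sites have two instructions that need reconciling.

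3. **The event is not lost.** This stands. It remains under Placebo-Lebri in the combined-period tables, and SAP 10.1 lists all AEs. Conjunctivitis has its own follow-up form (Protocol 10.6.1), summarised or listed under SAP 10.5.3, and an event that becomes serious also goes on an SAE form. The combined tables, however, pool placebo and lebrikizumab time and cannot show that the worsening followed the switch.

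4. **The incidence is right; only the grade moves.** For any-TEAE incidence up to Week 16 this stands, since the event did begin on placebo. Severity is also not among the safety endpoints in Protocol section 6. It is nevertheless tabulated under Protocol 11.8.4 and SAP 10.1.

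5. **The incomplete-date default is a small issue.** This is fair. It matters mainly for fully missing dates, year-only dates and dates in the month of the switch.

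A reader might also infer that every AE worsening after Week 16 is charged to placebo. Case b shows otherwise: an AE that began before the first dose is recorded at each severity.

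**Conclusion.** The gap is real but limited. It affects AEs that start after the first placebo dose and before the Week 16 injection, and that worsen on lebrikizumab. For these, the plan as written would show the severity reached on lebrikizumab in the placebo Induction column and no Maintenance TEAE. This rests on the one-record rule being applied as written and on placement by start date, which is inferred for complete dates.

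At most 104 planned placebo patients are exposed. The number affected cannot be estimated from the documents.

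A reader might conclude that the rule always works against detecting harm. The documents do not support that for the Week 16 contrast, because the same rule can raise Induction severity in the lebrikizumab arm and the net bias may be in either direction or nil. Within the placebo arm alone, both effects (higher severity on placebo, missing TEAEs after the switch) do obscure a change at the switch. The point is worth correcting because the Induction severity tables feed the only controlled safety comparison and the correction is small.

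**What to change.** **Protocol 10.6.2.** Extend the existing exception: an AE ongoing at the Week 16 injection that worsens afterwards is entered again with the new severity and its date. Do this in both arms, so that recording does not reveal who switched while Weeks 16 and 18 are still blinded. Reconcile the wording with 10.6.3 on reporting worsening.

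**SAP 10.1.** State that AEs are assigned to periods by the onset date of the record, and define Maintenance treatment emergence as new or worsened relative to the state at the Week 16 injection. The rule that a repeated AE counts once at maximum severity should then be applied within each period.

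**SAP 7.3.2.** Count a TEAE in both periods when its incomplete date cannot exclude onset after the Week 16 injection, as 7.3.3 does for medications.

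**Cost.** A small protocol change with matching eCRF guidance, a few SAP sentences, occasional extra AE rows and a few events shown in both periods. For patients already past Week 16, worsening dates would have to be recovered from source, because the AE record does not hold them.

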10.6.3 Recording of Adverse Events

AEs will be collected from the signature of the ICF/IAF up to 18 weeks after last study drug administration. Any AE reported by the patient from the last trial contact (follow-up telephone contact or visit) until Week 68, should be collected in the eCRF.

Medical disorders present at the time the patient signs the ICF/IAF that are part of the patient's medical history will only be considered AEs if they worsen after this time.

Abnormalities detected before IMP administration during physical examination, laboratory tests, or other safety assessments will not be considered AEs if already known as part of the medical history or in relation to prior medical conditions and will be recorded on the eCRF or case report form medical history/physical examination form/page. However, abnormalities detected in Screening/Baseline tests that are not part of the patient's medical history will be considered AEs.

Abnormalities (newly occurring or worsening of previously known abnormalities) detected after IMP administration during physical examination, laboratory tests, or other safety assessments, that are considered clinically relevant by the Investigator, that require an intervention or a diagnostic test, or may result in IMP discontinuation should be reported as AEs.

Reported terms should accurately characterise the AE. When a patient experiences an unspecified injury or signs and symptoms, an active investigation should be conducted to reach a final diagnosis. Disease diagnosis would be the preferred reported term.

AEs will be elicited by asking the patients non-leading questions (eg, "How do/did you feel?) and by collecting AEs spontaneously, as reported by the patient to the Investigator or designee.

All AEs elicited by the Investigator during the defined AE collection period must be recorded on the eCRF. In addition, when an AE meets the criteria of seriousness (ie, it is an SAE), it must also be recorded on the SAE form and reported following the defined timelines in [Section 10.6.4](#).

10.6.4 Reporting of Serious Adverse Events

Serious adverse events will be collected from signature of ICF/IAF up to 18 weeks after last study drug administration.

The Investigator must report any SAE within 24 hours from the moment she/he first learns of it to the Sponsor **PPD** pharmacovigilance unit on a SAE report form. This reporting will take place regardless of whether the Investigator considers the event to be causally related

to the IMP(s), to any other medicinal product(s), to the clinical trial procedure, or to any intervention undergone by the patient.

Original reports are to be kept by the Investigator in the Investigator's file.

The trial centre must transmit the SAE report form and pregnancy form to the following SAE email or fax number: [contact] or [contact]

Contact details and specific instructions on the flow of the SAE will be provided to all sites by the CRO.

The minimum information that must be included in the initial report is:

- An event meeting the criteria of SAE
- A qualifiable reporter, defined as an Investigator of this trial or his/her delegate
- A qualified patient, defined as a patient who has consented to participate in this trial
- A suspect medicinal product
- The Investigator's causality assessment

Unless the SAE has been sufficiently documented in the initial report, the Investigator will provide all available additional information in follow-up reports by using a new form and adhering to the same routing and time frames as defined for the initial report. This process will be continued until the event has been fully documented and reported.

An event reported to the Sponsor **PPD** pharmacovigilance unit that does not meet the SAE criteria shall be nullified by the Investigator by forwarding a follow-up report.

A regulatory report of the SAE (depending on the local requirements) will be produced by the Sponsor **PPD** pharmacovigilance unit and submitted to the Competent Authorities, IEC, and/or Investigators, when applicable according to local regulations.

SAEs NOT considered reportable to the Sponsor will be:

- Hospitalisation for a treatment/surgical procedure that was elective or pre-planned for a pre-existing condition that did not worsen during the participation in the trial
- Events that result in hospital stays for observation of <24 hours and that do not require a therapeutic intervention/treatment (eg, an emergency room visit for haematuria that results in a diagnosis of cystitis and discharge to home on oral antibiotics)

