10.6.1 Definitions

Adverse Event

An AE is defined as any untoward medical occurrence in a clinical trial participant, regardless of the administration of the IMP and its causal relationship to it.

An AE can therefore be any unfavourable and unintended medical occurrence during the patient's participation in the trial, including deterioration of a pre-existing medical condition, an abnormal value in a laboratory assessment, or an abnormal finding in the physical examination.

AEs must be temporally associated with the patient's participation in the trial; ie, occur after the patient signs the ICF/IAF. At the time of the occurrence of an AE, the administration of the IMP does not need to have been initiated yet. If initiated, it does not necessarily need to have a positive causal relationship to the event.

Adverse Events of Special Interest

The following TEAEs are being designated as Adverse Events of Special Interest (AESI):

- conjunctivitis
- herpes infection or zoster

The Investigator must report any AESIs within 48 hours from the moment she/he first learns of it to the Sponsor **PPD** pharmacovigilance unit. Additional data will be collected for AESIs during the treatment and follow-up phases. A specific follow-up form for conjunctivitis will be provided to the site. Patient records will include any follow-up information regarding these AESIs.

Serious Adverse Event

An SAE is an AE, that falls into 1 or more of the following categories:

- results in death
- is life-threatening (ie, an event that, in the view of the Investigator, places the patient at immediate risk of death from the event as it occurred.) It does not mean that the event might hypothetically have caused death if it were more severe or had lasted longer
- requires in-patient hospitalisation or prolongs existing hospitalisation
- results in persistent or significant disability or incapacity
- is a congenital anomaly or birth defect
- is any other medically important event that may jeopardise the patient or may require intervention to prevent one of the other above outcomes

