Medical and scientific judgment should be exercised in deciding whether or not other situations should be considered serious reactions, such as important medical events that might not be immediately life-threatening or do not result in death or hospitalisation, but may jeopardise the patient or may require intervention to prevent one of the other outcomes listed in the definition above, should also be considered serious. These are considered "other important Medical events."

Hospitalisation is defined as an overnight stay at the hospital or emergency room.

Prolongation of hospitalisation is defined as any extension of an in-patient hospitalisation beyond the stay anticipated/required in relation to the original reason for the initial admission, as determined by the Investigator or treating physician.

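### The protocol requires every SAE to go to the Sponsor within 24 hours, yet exempts untreated overnight observation stays under 24 hours, which its own definition makes SAEs

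*Protocol*

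**What the plan says.** Protocol 10.6.1 lists among the seriousness criteria an event that "requires in-patient hospitalisation or prolongs existing hospitalisation". It goes on: "Hospitalisation is defined as an overnight stay at the hospital or emergency room". No minimum number of hours and no treatment condition is attached.

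Protocol 10.6.3 says that "when an AE meets the criteria of seriousness (ie, it is an SAE), it must also be recorded on the SAE form and reported", and points to 10.6.4 for the timelines. Protocol 10.6.4 says: "The Investigator must report any SAE within 24 hours from the moment she/he first learns of it to the Sponsor", whether or not the event is thought to be related to the IMP. Neither sentence mentions an exception.

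The same section closes with a list introduced by the words "SAEs NOT considered reportable to the Sponsor will be". Its second item is "Events that result in hospital stays for observation of <24 hours and that do not require a therapeutic intervention/treatment", and the example given is "an emergency room visit for haematuria that results in a diagnosis of cystitis and discharge to home on oral antibiotics".

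**The concern.** An investigator with a patient kept overnight for observation, not treated, and sent home within 24 hours finds one instruction to report the event and another that it is not reportable. Both are in the current text, and both are in 10.6.4.

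What is at stake is mainly the expedited-reporting path. Under Protocol 10.6.5 the investigator judges causality, and the Sponsor or its designee then decides whether a 7-day or 15-day report is due. The exemption depends only on the length and purpose of the stay and the absence of treatment. It makes no allowance for an event that is considered related or is unexpected. A site that follows it need not send such an event to pharmacovigilance as an SAE. The adverse events of special interest are partly protected, because 10.6.1 gives them their own 48-hour reporting route.

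SAEs are also tabulated (SAP 10.1) and are to be reconciled between the clinical and drug safety databases (Protocol 12.2). Neither place says how to treat an SAE that was exempt from reporting.

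**Working it through.** The point rests on wording, so the check is whether one event can satisfy both rules. The inputs are the definition in 10.6.1, the general duty in 10.6.3 and 10.6.4, and the two conditions of the exemption in 10.6.4: an observation stay under 24 hours, and no treatment required. The 12-hour stay is only an illustration; any overnight stay under 24 hours gives the same answer.

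| Case | Hospitalisation under 10.6.1? | General duty to report? | Exemption met? | Result |
|---|---|---|---|---|
| Overnight observation, about 12 hours, no treatment | Yes | Yes | Yes | Both rules apply: conflict |
| Overnight, about 12 hours, treatment required | Yes | Yes | No | Report |
| Observation of 24 hours or more, including a night, no treatment | Yes | Yes | No | Report |
| Same-day observation, no night, no treatment | No | Not on this criterion | Conditions fit | Not an SAE on this criterion, so nothing to exempt |
| The protocol's example: emergency-room visit, home on oral antibiotics | No night mentioned | Not on this criterion | On a plain reading no, because it was treated | Illustrates neither rule |

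Three things follow.

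1. The overlap is real but confined to the first row. Both conditions of the exemption are needed; dropping the no-treatment condition would overstate it.
2. The first row is also where the SUSAR path can be cut. If such an event is considered related and is unexpected, it meets the criteria in 10.6.5, yet the list in 10.6.4 says it need not be sent.
3. The example does not help a site find the boundary. It ends in a prescribed treatment and mentions no overnight stay, so it does not show what the exemption covers. It leaves open whether a prescription at discharge counts as treatment.

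No figure in the plan needs to be reproduced. The sample size and the primary analysis do not depend on this wording.

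**The case against.** The best defence is that this is a general rule followed by its exception. The list sits in the same section as the duty to report, and its heading calls the listed events SAEs and removes only their reporting to the Sponsor. On that reading SAE status is untouched and the protocol says what it means. This largely stands as an account of intent. It does not repair the text: 10.6.3 and the 24-hour sentence in 10.6.4 are unqualified, and 10.6.3 refers to 10.6.4 for timelines, not for exceptions. Even if the exception is deliberate, its consequence for related, unexpected events remains.

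The example can be read more kindly, as no intervention needed during the stay and a prescription on leaving. That is possible, but a site should not have to guess it. Protocol 10.6.4 also promises sites specific instructions on SAE flow from the CRO. Those may settle the matter in practice; they are not among the documents.

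A reader might go further and infer four things that the documents do not support:

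- **That SAE rates will be understated.** All AEs go in the eCRF under 10.6.3, and nothing in SAP 10.1 makes reporting to the Sponsor a condition for being counted. One patient is 1/208 = 0.48 percentage points of the planned lebrikizumab arm or 1/104 = 0.96 points of the placebo arm, but that holds for any event and does not measure this problem.
- **That the arms will be compared unfairly.** The Induction Period is double-blind, no mechanism for arm-dependent reporting is apparent, and SAEs are summarised descriptively.
- **That hypersensitivity reactions will be lost.** Any that need treatment fall outside the exemption, and the documents do not say how often they lead to untreated overnight observation.
- **That the databases will be left unreconciled.** Protocol 12.2 requires reconciliation, with procedures in a Data Management Plan that is not available here. A mismatch is possible, not shown.

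**Conclusion.** Wrong as written, and minor. The definition of hospitalisation and the exemption overlap for untreated overnight observation stays under 24 hours. For those events the protocol both requires and waives reporting to the Sponsor. If the exemption is followed, some protocol-defined SAEs, possibly including related and unexpected ones, need not reach the pharmacovigilance unit as SAEs for the assessment in 10.6.5. The exemption's example does not fit its own condition on a plain reading.

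The size cannot be put in numbers: the documents give neither an SAE rate nor a frequency for such stays, and the category is narrow. The conclusion assumes that sites work from the protocol text and that the CRO's instructions do not already resolve the conflict. It concerns a safety-reporting rule only. Efficacy and sample size are not affected.

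**What to change.** Reconcile Protocol 10.6.1, 10.6.3 and 10.6.4:

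1. Either word the hospitalisation definition and the exemption so that they do not overlap, or keep the exemption and state it expressly as an exception in 10.6.3 and in the 24-hour reporting sentence of 10.6.4. The documents do not settle which rule should prevail, so that choice is the Sponsor's.
2. Remove the antibiotic example, or replace it with one that meets the exemption's conditions.
3. State that any exempted event meeting the 10.6.1 definition is still flagged serious in the eCRF, is counted in the SAE tables of SAP 10.1, and is sent to the Sponsor if considered related to the IMP.

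The cost is a few sentences in the protocol, a letter to sites, and a matching line in the CRO's SAE instructions if they differ. The downside is a few more SAE forms.
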